Study Duration	Each subject's participation will last 6 months. The entire study is expected to last five years.
Study Phases	(1) Screening : screening for eligibility and obtaining consent and (2) Baseline assessment
Screening	(3) Intervention : study intervention/experimental treatment. (4) Follow-up assessment will
Study Treatment	occur at 3 and 6 months.
Follow-Up	
Efficacy Evaluations	Results of the optimization experiment will be used to determine which combination of components and component levels contribute most significantly to mean weight loss (primary) and achievement of 5% weight loss (secondary) at 6 months.
Pharmacokinetic Evaluations	NA
Safety Evaluations	All medical events and safety data will be assessed at assessment points or when interim events are reported by participants using a standard form used in our ongoing NIH funded trials.
Statistical And Analytic Plan	The primary outcome analysis will use mixed effects models to test for differences in weight by intervention components across time (baseline, 3, and 6 months). ²⁴ Effects will be modeled as component x time interactions with the 6-month outcome as the primary endpoint. All higher-order interactions between components will be modeled. Additional models will evaluate the likelihood of reaching 5% weight loss at 6 months.
DATA AND SAFETY MONITORING PLAN	Data safety management in this trial is intended to achieve 4 objectives: 1) to minimize the occurrence of adverse effects, especially those related to intervention; 2) to effectively

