To equate frequency of message delivery across all conditions, all participants will receive 10 messages per week (1-2 messages per day), between 8:00AM and 9:00PM. Participants will receive a smartphone notification when a new message is displayed in the app. The messages are displayed on the Home page of the AGILE app and remain there until they expire at midnight. Participants can like or dislike messages with a thumbs up/thumbs down. Messages pertain to one of three behaviors (eating, activity, self-weighing) and are chosen based on decision rules that evaluate participant behavioral data at the time the rules are evaluated. A pre-determined schedule (which varies by some of the components as described below) assigns 1-2 behaviors that will be messaged on each program day, with unique decision rules for each behavior. Most intervention messages include one or two of the following message types: feedback on outcome, feedback with a data point, directive action, nondirective action, encouragement/motivation, and social comparison. Other intervention messages are short interactive action planning tools that guide the participant to develop a plan for one of their behavioral goals.

Description of Intervention Components (Factors)

Dietary Self-Monitoring Approach. Participants in this trial will be randomly assigned to a Standard or Simplified approach. Participants assigned to Standard tracking will receive a calorie goal ranging from 1425-2850 per day based on their sex and starting weight and will track their calories using the Fitbit app, which transmits to the study servers via the Fitbit API. The Simplified “red” food (RF) approach focuses on reducing overall caloric intake by tracking and reducing intake of RFs only; there are no specific goals for green and yellow foods. Participants assigned to Simplified tracking will receive a daily RF limit that ranges from 3-6 RFs per day and will track their RFs in a native Traffic Light Log app created for this study. They are not required to track their green and yellow foods but can do so if they choose. Participants will be able to see their current and historical dietary progress on the Eating page of the AGILE app, which will display RFs for the Simplified group and calories for the Standard group.

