4. STATISTICAL CONSIDERATIONS

Sample Size and Power

We defined a 1-kg weight change as more than a minimal effect of any given component on overall weight loss. We estimated standard deviation based on a prior cell phone-delivered intervention for YAs that found a standard deviation of 6.9 kg for a weight change difference of 2.2 kg between groups;⁹ therefore, we conservatively estimated a standard deviation of 4 times our 1-kg weight change estimate. Assuming a type 1 error rate of 5% and a standard deviation of 4 kg, reaching 80% power would require 505 total participants. Assuming a 17% attrition rate at 6 months based on our previous studies with YAs and rounding up to a whole number per condition results in a total of 608 participants needed. Thus, each of the two levels of each component will have 304 randomly assigned participants, with 19 participants in each of the 32 conditions.

Statistical Analysis

Aim 1 Analysis. To test for differences in weight change across time by the five intervention components, we will use mixed effects models on an intention-to-treat data set, with effects modeled as component \times time interactions and the 6-month outcome as the primary endpoint. We will run separate models for (a) mean weight change and (b) the proportion of participants achieving 5% weight loss, the latter constituting a second-level decision-making criterion in cases where effects for mean weight change are equal. All higher-order interactions between components will also be modeled (e.g., adaptive physical activity goals \times message choice \times time interaction). The ability to test all higher-order interactions between intervention components, without reducing power, is a key advantage of the factorial experiment, as this is not possible in a traditional multi-component RCT. We will be using effect (-1,1) coding rather than dummy (0,1) coding, which keeps any covariances among main effects and interactions to a minimum. Once we have identified important effects in the initial set of models, we will establish parsimonious prediction models in which coefficients that do not contribute significantly to mean weight loss (or proportion achieving 5% weight loss) will be set to zero.

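### The Aim 1 mixed model does not say how baseline weight is used; a common-baseline model with sex as a covariate would give a small, free gain in precision and fix the covariance structure

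*Combined protocol and SAP*

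**What the plan says.** The synopsis (Statistical And Analytic Plan) describes "mixed effects models to test for differences in weight by intervention components across time (baseline, 3, and 6 months"), so baseline weight is one of the modelled responses. Section 4 (Statistical Analysis, Aim 1) says "we will use mixed effects models on an intention-to-treat data set, with effects modeled as component" by time interactions, with 6 months as the primary endpoint. It uses effect coding and includes all higher-order interactions. Neither place lists or excludes covariates, says whether components may differ at baseline, or names a covariance structure.

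Baseline characteristics have other roles. Gender, race and ethnicity, and initial BMI are exploratory moderators in Aim 3, and auxiliary variables may be used for imputation (Handling Missing Data). In section 2, participants assigned to standard diet tracking receive a "calorie goal ranging from 1425-2850 per day based on their sex and starting weight".

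The sizing statement is "Assuming a type 1 error rate of 5% and a standard deviation of 4 kg, reaching 80% power would require 505 total participants", for a 1-kg component effect. The SD is introduced with "we conservatively estimated a standard deviation of 4 times our 1-kg weight change estimate", and no credit is taken for covariate adjustment.

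Section 3 is inconsistent about 3 months. The primary-outcome paragraph has weight measured at every time point, while the Data Collection paragraph limits the 3-month assessment to psychosocial measures and medical events.

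**The concern.** Having baseline weight in the response vector is not the same as conditioning on it. If the model keeps a component effect at baseline, the component by time coefficient at 6 months reproduces the change-score comparison. Whatever starting weight and sex could explain of the kilograms lost then stays in the residual. Randomisation makes the baseline means equal in expectation, so imposing that equality is legitimate and recovers the precision of an analysis adjusted for baseline weight.

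The stakes are modest but concrete. The model produces 31 component effects (2^5 - 1) at 6 months. Planned power for a 1-kg effect is about 80%, and terms that are not significant are set to zero in the final prediction models. Leaving the baseline handling and covariance structure open also leaves a choice among models with different standard errors, made after the data are in.

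**Working it through.** **Inputs from the documents (section 4).** Effect 1 kg, SD of change 4 kg, type I error 5%, power 80%, 505 analysed, 608 randomised, 1:1 allocation within each component. Sidedness is not stated; two-sided is used because it reproduces 505 (one-sided gives 396).

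**Assumed inputs (not in the documents).** Baseline weight SD 12-18 kg with equal variance at baseline and 6 months. As an alternative, baseline SD 15-20 kg with loss equal to 3-5% of starting weight. For the covariance check, change SDs of 3 kg at 3 months and 4 kg at 6 months, correlated 0.75.

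**1. The plan's own figure.** Total N = 4 x [4 x (1.960 + 0.842) / 1]^2 = 502.3, or 252 per level and 504 in total. The noncentral t version gives exactly 505 (power 80.0% with 32 model terms). 505/0.83 = 608.4, in line with 608. The sizing reproduces with no adjustment.

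**2. Baseline effects free.** The standard error of the difference between two levels is 2 x 4/sqrt(505) = 0.356 kg. A generalised least squares calculation with weight at baseline and 6 months as responses, and a component effect allowed at baseline, returns the same 0.356 kg. (With -1/+1 coding the regression coefficient is half the level difference.)

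**3. Common baseline mean.** Let rho be the correlation between baseline and 6-month weight. Then rho = 1 - SDchange^2/(2 x SDbaseline^2), and the variance ratio to the change-score analysis is (1 + rho)/2.

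| Baseline SD | rho | Variance ratio | SE (kg) | Power at 505 |
|---|---|---|---|---|
| Not used | - | 1 | 0.356 | 80.0% |
| 12 kg | 1 - 16/288 = 0.944 | 0.972 | 0.351 | 81.1% |
| 18 kg | 1 - 16/648 = 0.975 | 0.988 | 0.354 | 80.5% |

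The constrained fit and a regression adjusted for baseline weight give the same standard errors.

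**4. Alternative assumption.** The variance reduction is r^2, where r is the correlation of baseline weight with change.
- Low end: r = 0.03 x 15/4 = 0.11, reduction 1.3%.
- High end: r = 0.05 x 20/4 = 0.25, reduction 6.25%. The SE is 0.356 x sqrt(0.9375) = 0.345 kg and power is 82.5% (same noncentral t calculation).
- In completers, 505/(1 - r^2) - 505 is about 6 to 34.

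**5. Other covariates.** If all baseline covariates together explained 5% or 10% of the variance of change, power would be 82.0% or 84.0%. The documents give no such figure, for sex or for anything else.

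**6. Covariance structure.** A random-intercept-only fit to three weights pools the three pairwise change variances. These are 9 (baseline to 3 months), 16 (baseline to 6 months) and 9 + 16 - 2 x 0.75 x 3 x 4 = 7 (3 to 6 months). Their mean is 32/3 = 10.67, against the true 16 for the 6-month change. The SE ratio is sqrt(10.67/16) = 0.816, so the reported SE is 18% too small. Type I error becomes 2 x [1 - Phi(1.96 x 0.816)] = 11.0%, and simulation agrees at about 11%. For a 3-month SD of 2.5-3.5 kg and a correlation of 0.6-0.85, the range is 7.5-13.8%. With complete weights at baseline and 6 months only, the random-intercept model gives the change-score SE and there is no inflation.

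**The case against.** The strongest reply is that the plan is silent rather than wrong. Component by time terms are compatible with a common baseline mean, and mixed models include unstructured covariance. That stands: the precision loss follows from one reading of the model, not from anything the text commits to. A reader might infer that covariates have been ruled out, but the documents do not say so.

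A reader might also infer that the trial is underpowered by this omission. It is not. The 505 rests on an unadjusted SD and reproduces, so adjustment would be a bonus.

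Chance imbalance is not a serious threat either. With 304 per level and baseline SD 15-20 kg, the SE of the baseline difference is 2 x SD/sqrt(608) = 1.2-1.6 kg. At 3-5% loss, one such SE moves the contrast by about 0.04-0.08 kg against a 1-kg target. This is not bias, since the unadjusted standard error already includes it.

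The calorie-goal rule is weak evidence that kilograms lost depend on sex and starting weight. It applies only to the standard diet-tracking level, and scaling a goal to the person does not show that the outcome follows.

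Finally, the 11% error rate could be read as a property of the planned analysis. It is conditional. The plan does not specify a random-intercept-only model, the inputs are assumed, and it is unclear whether 3-month weights will exist.

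What survives is that the more precise model is identifiable now, uses data already collected, and has no real downside for the continuous outcome.

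**Conclusion.** The point holds as a low-cost improvement. As written, the Aim 1 model can be fitted so that the 6-month contrast ignores starting weight. Specifying a common baseline mean removes about 1-3% of variance (80.0% to about 80.5-81.1% power) at an assumed baseline SD of 12-18 kg with equal variances. It removes up to about 6% if baseline weight correlates 0.25 with change. All of this takes the planned 4-kg SD of change as given. Any gain from sex is unquantified.

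Naming the covariance structure is a safeguard for validity. It matters only if three weights are analysed and a random-intercept-only fit would otherwise be chosen.

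**What to change.** In section 4 (Aim 1) and the synopsis, specify a baseline-constrained repeated-measures model:
- a common baseline mean, with no component terms at baseline;
- effect-coded component by time terms, including the planned interactions, at each post-baseline visit;
- unstructured covariance;
- sex by time as a covariate.

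The equivalent single-endpoint form is a regression of 6-month change on the effect-coded components plus baseline weight and sex. With incomplete data the two can differ slightly, so name one as primary.

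Reconcile the two statements in section 3 on whether weight is collected at 3 months, and set the model's time points to match.

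Adjusting the 5% weight-loss model is optional. That outcome is already scaled to starting weight, no link function is stated, and with a logistic link covariates change the odds ratio being estimated. If adjustment is wanted, state the target quantity.

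The cost is analysis-plan wording only: baseline weight and demographics are already collected, and the sample size does not change. The change should be fixed before outcome data are examined.

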To improve weight, multiple daily behavioral targets are needed, including dietary intake, physical activity, and self-weighing. Thus, for weight loss, automated mobile interventions must be able to provide tailored, adaptive messaging that considers participants' behavioral contexts across all weight-related behaviors and sends the "right" message for the "right" behavior and at the "right" time. However, the level of tailoring provided in messaging exists along a continuum, and it is not yet known how much tailoring and adaptation is needed to be effective. Moreover, there are other components of automated interventions that could increase engagement or effectiveness, including adaptive goal setting and alternative methods of self-monitoring, but few studies have examined alternatives among YAs. We conducted a pilot 12-week remotely delivered JITAI that delivered up to 4 messages per day to young adults in a mobile behavioral weight loss program and found that participants viewed 68% of messages, and viewing messages was associated with increased likelihood of reaching daily behavioral goals.¹⁸ While this was promising, many questions remain about how adaptive and personalized a JITAI needs to be to be effective for weight loss in YAs.

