1. STUDY OBJECTIVES

To address evidence gaps regarding JITAIs, the objective of this trial is to simultaneously test innovative or adaptive intervention components, compared to their standard counterparts, that are expected to increase weight loss among YAs. This is an optimization trial, conducted as part of the Multiphase Optimization Strategy (MOST) framework.²⁴ Guided by Self-Determination Theory (SDT),²⁵ the trial will test 5 components that are designed to promote positive changes in SDT constructs: 1) diet self-monitoring approach (standard vs. simplified), 2) adaptive physical activity goals (weekly vs. daily adaptive), 3) decision points for message timing (fixed vs. adaptive), 4) decision rules for message content (standard vs. adaptive), and 5) message choice (no vs. yes).

Aim 1: Build an optimized JITAI consisting of the set of intervention components (and component levels) that yield the greatest improvement in weight change among young adults at 6 months. We will use a highly efficient experimental design, powered to detect both main effects and all two-way interactions between components. Results of the optimization experiment will be used to determine which combination of components and component levels contribute significantly to mean weight loss at 6 months. The proportion achieving 5% weight loss is our second-level decision-making criterion in cases of equal weight losses.

Aim 2: Conduct mediation analyses to test the relationships between the intervention components and hypothesized mediators. Mediators to be tested include the proximal theoretical mediators of component effects (self-regulation, competence, relatedness, relevance, autonomy) and the more distal behavioral mediators (dietary intake, physical activity, and daily self-weighing).

Aim 3: Conduct moderation analyses. The primary moderator to be tested is intervention engagement including self-monitoring engagement (weighing frequency, diet monitoring, tracker wear) and app engagement (app views, lessons, feedback, intervention message views). Exploratory moderators include gender, race/ethnicity, and initial BMI status.

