Adaptive Activity Goals (Weekly Adaptive versus Daily Adaptive). Adaptive intervention components, such as adaptive physical activity goals, may support more precise shaping of an individual’s behaviors, improve adherence, reduce treatment mismatch, and increase competence.³⁵ *Perceived competence*, or an individual’s feelings about their capabilities with respect to a behavior, has been shown to be an important predictor of weight loss,³⁶ and adoption and maintenance of physical activity.³⁷ The current standard for physical activity goal progression, in the context of weight loss, is to gradually increase goals with a fixed progression over time, regardless of an individual’s previous goal achievement, which may not be optimal for promoting behavior change³⁸ or supporting an individual’s competence related to physical activity. Adaptive goal setting, in which the goals are set based on participants’ personal activity levels, is emerging as an alternative to fixed progression goals,^{38,39} with evidence that interventions with step goals that adapted on a daily basis improved steps/day compared to static step goals.³⁸⁻⁴⁰ However, it is unclear whether this daily frequency of goal adaptation (“Daily Adaptive”) is necessary for a daily activity goal and whether it is more effective than adapting goals on a weekly basis (“Weekly Adaptive”).

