Decision Rules. Participants will be randomly assigned to standard decision rules or adaptive decision rules. In standard, the decision rules include a limited set of variables representing behavioral progress from the current and prior day. In addition, participants are eligible to receive an interactive action planning tool if they are in a 2-day lapse, meaning they have not met their goal the current or prior day. In adaptive decision rules, the rules mirror the fixed rules, with additional behavioral and contextual tailoring variables that allow for consideration of past progress on the given behavior, other behaviors, and recent weight change, such that a message about a different behavior can be sent if that might be more appropriate for the participant. Also, participants in adaptive decision rules are not eligible to receive an interactive action planning tool unless they are in a behavioral lapse of at least 4 days (compared to 2 in standard). These additional tailoring variables and adjustments are designed to provide flexibility in the messages that can be sent to participants. Rather than requiring that the system send a message about the behavior that was assigned for that day, the comprehensive rules allow the system to, when needed, send a message on another behavior that would be more appropriate. As an example, a fixed decision rule for eating may evaluate yesterday's dietary goal achievement, the current day's dietary tracking, and current dietary intake compared to their goal. If the participant has tracked nothing, they will receive a message prompting them to track their foods. In adaptive decision rules, the rules will also evaluate recent goal progress and weight change, such that a participant who regularly tracks their food intake and is losing weight would not receive this reminder message; instead the system would choose a message about a different behavior. However, these messages would be delivered if this pattern repeated, or if the weight trajectory was no longer favorable.

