- Treatment Self-Regulation (ACM). The Treatment Self-Regulation Questionnaire (TSRQ) will be used to assess autonomous and controlled motivation for making changes in diet (15 items) and physical activity (15 items).⁷⁰ Examples item: “Because I feel that I want to take responsibility for my own health” answered on a scale of 1 (*not at all true*) to 7 (*very true*).

Other Psychosocial and Behavioral Measures (collected at baseline, 3, and 6 months)

- Quality of Life. All participants will complete the CDC Health-Related Quality of Life measure (referred to as “Healthy Days Measures”).¹³⁶ This 4-item questionnaire reliable, valid, and responsive to change.
- Depression (ACM). Depressive symptoms have been associated with changes in weight, diet, and physical activity and will be assessed with the Center for Epidemiological Studies Depression Scale (CES-D).¹³⁷
- Weight Control Strategies (ACM). Participants will be asked about frequency of use of 20 weight control strategies such as “ate only when I was hungry” with a scale used in the EARLY trials.¹³⁸
- Hunger, Restraint, Disinhibition. The Three Factor Eating Questionnaire (TFEQ) is a 51-item self-report instrument assessing three factors of dietary restraint, disinhibition and hunger.¹³⁹
- Perceived Stress (ACM). The Perceived Stress Scale is a 10-item measure that assesses stressful situations in the last month.¹⁴⁰
- Binge Eating (ACM). Participants will complete the revised Questionnaire on Eating and Weight Patterns (QEWP-5) to assess frequency of binge eating, loss of control, and compensatory behaviors.¹⁴¹

Process and Adherence Measures (collected over 6 months)

- Dietary Monitoring. Objective self-monitoring of dietary intake will be assessed using data from the smartphone application food log (for simplified conditions) and Fitbit food log (for calorie conditions).
- PA monitoring. Objective self-monitoring of PA will be assessed via the Fitbit tracker data. Using the Fitbit API, the study will collect data on the number of days the Fitbit was worn (steps $\geq 500/\text{day}$).⁹⁵
- Self-weighing. Self-weighing habits will be objectively measured via the smart scales to calculate percent of days weighed, and average self-weighing days per week.

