Aim 2 Analysis. In Aim 2 we will conduct mediation analyses to test the relationships between the intervention components and hypothesized mediators, thus refining the underlying conceptual model. In contrast to mediation analyses conducted on data from an RCT, we will be able to fit models specifying which intervention component is mediated by each hypothesized mediator. For example, while we hypothesize that autonomy will mediate the relationship between the intervention component, message choice, and weight, it is possible that other mediators—e.g., relatedness—will explain this relationship. It is also possible that autonomy will mediate the relationship between other intervention components (e.g., decision points for message timing) and weight. This step will provide important information for improving our understanding of how the intervention components work and for revising our conceptual model. Mediators to be tested include the proximal theoretical

mediators of component effects (self-regulation, competence, relatedness, relevance, and autonomy) and the more distal behavioral mediators (daily self-weighing, dietary intake, and physical activity). We will test the mediation effects for significance using the general approach described in MacKinnon.

Aim 3 Exploratory Analyses. In Aim 3 we will conduct moderation analyses to test differential response to intervention components. The primary moderator to be tested is intervention engagement, which will include percentage of messages viewed, number of days of diet self-monitoring, number of days of physical activity tracking, number of days of self-weighing, and lessons viewed. Exploratory moderators will include gender, race and ethnicity, and initial BMI status. Results will provide important information for future research aimed at developing mobile interventions tailored and optimized for differing levels of engagement and subgroup membership.

Handling Missing Data

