All recruitment efforts will direct participants to a study website with a more detailed description of the research study and FAQs about participating in research. Interested individuals will click through to a REDCap web screening survey to determine initial eligibility. Those who are preliminarily eligible will be contacted by trained study staff and will undergo additional phone screening. Following an approach we have used in the past, eligible and interested individuals will receive an email directing them to a unique REDCap link to an online informed consent. After providing consent, participants will be instructed on procedures for 1) completing one weekday and one weekend self-reported 24-hour dietary recall, 2) completing baseline online questionnaires, and 3) completing their baseline weight measurement using a Bluetooth-connected scale. The Fitbit scale and activity tracker will be mailed to the participant. After completion of baseline assessments, the participant will be randomized to one level of each of the 5 factors, or one of the 32 conditions (Table 1). The participant will be scheduled for a one-on-one telephone/videochat session during which they will be informed of condition assignments, assisted with downloading of the study smartphone app, and questions about getting started will be answered.

Inclusion of Women and Minorities

All individuals will be eligible for enrollment independent of sex/gender and race/ethnicity. As women are generally over-represented in weight control studies, we do not anticipate having inadequate representation by women. To be able to test for differences in the treatment effect by sex/gender, we may need to specifically target recruitment of men. Our research group has had success in recruiting higher percentages of men by using pictures of men in Facebook/social media advertisements, and by using terms such as “wellness” and “health” instead of “weight loss.” Therefore, we will use these strategies to increase our recruitment of men if we are under our targets.

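### Aim 3's primary moderator, engagement, is measured after randomization and may be changed by the components, so component-by-engagement results cannot be read as differential response

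*Combined protocol and SAP*

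**What the plan says.** The purpose of Aim 3 is given in Section 4 (Aim 3 Exploratory Analyses): "we will conduct moderation analyses to test differential response to intervention components". The same paragraph names the moderator: "The primary moderator to be tested is intervention engagement, which will include percentage of messages viewed, number of days of diet self-monitoring", and adds days of activity tracking, days of self-weighing and lessons viewed. Section 1 (Study Objectives, Aim 3) agrees: "The primary moderator to be tested is intervention engagement including self-monitoring engagement (weighing frequency, diet monitoring, tracker wear". Gender, race/ethnicity and initial BMI are listed as further, exploratory moderators. The results are meant to inform future research on interventions adapted to a person's level of engagement.

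On timing, Section 7 (Recruitment) says: "After completion of baseline assessments, the participant will be randomized to one level of each of the 5 factors". Section 3 lists the diet, activity and weighing measures under "Process and Adherence Measures (collected over 6 months".

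On whether components may alter engagement, Section 1.3 says: "there are other components of automated interventions that could increase engagement or effectiveness, including adaptive goal setting and alternative methods of self-monitoring". Section 4 (Aim 2) also lists daily self-weighing as a behavioral mediator, that is, as something the components may change.

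**The concern.** Randomization makes the two levels of a component comparable overall, and comparable within subgroups defined by baseline variables. It does not do so within subgroups defined by behavior that follows assignment. If a component changes that behavior, high engagers at one level are a different kind of participant from high engagers at the other. Two separate errors can follow.

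- **(a) Shift.** If the component moves everyone's engagement, its estimated effect at a given engagement level is biased. The interaction test itself is largely unharmed.
- **(b) Changed link.** If the component changes who engages, or how engagement is recorded, the interaction test can show moderation that does not exist, with or without a shift.

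Several design features could produce one or the other. Diet-monitoring days come from the study food log at one diet level and the Fitbit log at the other (Section 3). Under adaptive decision rules, "a participant who regularly tracks their food intake and is losing weight would not receive this reminder message" (Section 2). Adaptive timing can move a message to later in the day while all messages expire at midnight (Section 2), so time available for viewing could differ even though the number sent is equal.

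At stake is the Aim 3 reading. A component that works equally for everyone could be reported as working mainly in high or in low engagers. One that helps a little by raising engagement could look harmful at a fixed engagement level.

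**Working it through.** **The plan's own figure.** Section 4 gives a 1 kg effect, SD 4 kg, type 1 error 5% (taken as two-sided) and 80% power. Per level, n = 2 × (1.96 + 0.8416)² × 4² / 1² = 251.2, so 252, or 504 in total against the stated 505. Then 505 / 0.83 = 608.4 against 608. The figure reproduces. It concerns main effects; no figure is given for Aim 3.

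**Assumptions for the illustration.** From the plan: N = 505 and SD 4 kg. Assumed, because the documents are silent: an unmeasured motivation score correlated r = 0.5 or 0.3 with weight loss, and correlated ρ with engagement. The component has no effect on weight unless stated. Positive values mean less weight loss.

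**(a) Shift only.** If the component raises engagement by s SD, participants at the same engagement level differ in mean motivation by ρ × s, so

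bias = ρ × s × r × SD.

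| s (ρ = 0.5) | r = 0.5 | r = 0.3 | Simulated |
|---|---|---|---|
| 0.3 | 0.5 × 0.3 × 0.5 × 4 = +0.30 kg | 0.5 × 0.3 × 0.3 × 4 = +0.18 kg | +0.287 / +0.173 kg |
| 0.1 | +0.10 kg | +0.06 kg | +0.094 / +0.053 kg |

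The simulation used 6,000 trials per scenario, with tracking days limited to 0–182. At s = 0.3 the component effect at fixed engagement rejected in 12.7% / 8.5% of trials; the interaction rejected in 5.1% / 5.1%.

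Now let tracking itself lower weight by 0.5, 1.0 or 1.5 kg per SD. The true component effect becomes −0.15, −0.30 or −0.45 kg for everyone (0.3 × each value). The estimate at fixed engagement remains +0.17 to +0.29 kg, so the sign is reversed.

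**(b) Changed link, no effect on weight.** If ρ differs between levels by Δ, the false difference in slopes is Δ × r × SD. Its standard error is about 2 × 4 / √505 = 0.356 kg per SD of engagement.

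| Δ | False interaction, r = 0.5 / 0.3 | Approximate rejection | Simulated range |
|---|---|---|---|
| 0.1 | 0.20 / 0.12 kg | 9% / 6% | 6–9% |
| 0.2 | 0.40 / 0.24 kg | 20% / 10% | 10–22% |

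The simulated ranges cover several pairs of links, with and without a shift. For links 0.6 and 0.4 without a shift, rejection was 20.1% / 10.7%, while a direct test of the component on engagement rejected only about 5%. A null engagement test therefore does not clear the moderation result.

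**Measurement and reminder rule.** Food logs of unequal reliability, with true tracking unchanged, gave false interaction rates of 5–6% (0.9 versus 0.8), 5–10% (0.9 versus 0.7) and 6–16% (0.9 versus 0.6). The withheld-reminder rule modelled alone gave 5–6%, with a bias of 0.02 to 0.23 kg at fixed engagement.

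**Larger changes.** A second simulation (4,000 trials) used stronger inputs: a one-unit shift, which is 1/√2 = 0.71 SD, and motivation slopes of 1.5 versus 0.5. False effects within the low or high half of engagement reached 0.3 to 1.8 kg in size, and the interaction rejected in up to 25% of trials.

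**Baseline moderator.** A pre-randomization measure correlated 0.7 with motivation kept the interaction test at 4.8–5.4% in all 24 scenarios.

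**The case against.** The strongest reply is that Aim 3 is headed exploratory, feeds only future research, and leaves Aim 1 alone. That limits the consequence. But an exploratory label warns about certainty and multiplicity; it does not tell readers that the contrast is not a randomized one.

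Some of the evidence that components change engagement is weak, and this stands in part. The statement that adaptive components may "improve adherence, reduce treatment mismatch, and increase competence" is about adaptation in general, whereas both activity-goal levels here are adaptive; Section 2 calls the benefit of daily over weekly adaptation unclear. The remark in Section 1.3 on adaptive goals has the same limit. The diet pilots found similar adherence. Under the reminder rule another behavior is messaged instead, and the reminder returns if the pattern repeats. Different logs need not differ in reliability. The documents thus show that changed engagement is possible, not that it will occur.

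It is also fair that error (a) leaves the interaction test near 5%, and that the plan does not say it will report component effects at fixed engagement. Probing a moderation finding, or describing results for high and low engagers, would normally produce those effects.

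Finally, baseline substitutes have low power. If the component effect truly varies by 0.5 kg per SD of an engagement trait, then with the 0.356 kg standard error power is about 29% with perfect measurement, 17% with a proxy correlated 0.7, and 7–11% at 0.3–0.5. This stands as a cost of the remedy. It does not make the post-randomization analysis valid.

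**Conclusion.** The concern holds. The timing is documented, the plan itself treats engagement or self-weighing as something components may change, and it offers neither a causal method nor a non-causal caveat. With modest assumed inputs the bias at fixed engagement is 0.02 to 0.29 kg, below the plan's 1 kg effect, and the false-positive rate of the interaction runs from about 5% to 22%. Values near or above 1 kg need much larger assumed changes. All sizes are illustrative; the structural point does not depend on them. Aim 1 component selection and the planned baseline moderators are unaffected, so this is a correction that should be made rather than a threat to the primary conclusion.

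**What to change.** In the Aim 3 text:

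1. Analyse each engagement measure as an outcome of each randomized component. Aim 2 already implies this for self-weighing only.
2. Keep the engagement-by-component weight results, but label them descriptive and non-causal, and state that they are not evidence of differential response. Say that a null result in step 1 does not lift this caveat.
3. Base tests of differential response on pre-randomization variables already collected: the planned gender, race/ethnicity and initial BMI, plus baseline self-regulation, competence and self-reported physical activity. Acknowledge their low power and the added number of tests.
4. State whether the run-in mentioned in Section 2 (Adaptive Activity Goals) precedes randomization. If it does, run-in tracker data would be a closer proxy for engagement than questionnaires.

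The cost is SAP wording and a set of simple models, with no new data or participants. The drawback is that baseline variables answer a related but different question from actual engagement.
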